Grade 3 or Higher Slit Lamp Findings (SLFs)

Grade 3 or Higher SLFs related to study lens wear will be converted to a binary response as $YY = 1$, if a subject eye has a clinically significant SLF, and $YY = 0$ otherwise, for analysis purposes. From the historical data there was *none or an extremely low rate* ($< 1\%$) for clinically significant SLFs (Grade 3 or higher) for the test lens. Assuming a correlation of 0.70 between left and right eyes within the same subject, a total of 5000 replicating trials were simulated with a reference rate of 2% (worse-case scenario). Given the rare event binary outcome of slit lamp findings, each replicated sample was analyzed using a Bayesian beta-binomial model with correlated binary data (Diniz et al; 2010).⁸ For each simulated trial, the upper bound of the 95% central posterior credible interval constructed for the percentage of grade 3 or higher SLFs for the test lens was compared to a margin of 5%. With the proposed sample size, at least 99% of the estimated 95% credible intervals had the upper bound below 5%.

Acceptable Lens Fitting

Acceptable lens fitting will be converted to a binary response as $YY = 1$, if a subject eye has acceptable lens fitting, and $YY = 0$ otherwise, for analysis purposes. As indicated in the historical data of these lenses there was an extremely high rate ($> 99\%$) acceptable lens fitting for the test lens. Assuming a correlation of 0.70 between left and right eyes within the same subject, a total of 5000 replicating trials were simulated with a reference rate of 99% (worse-case scenario). Given the rare event binary outcome of $Y=0$ (unacceptable lens fitting), each replicated sample was analyzed using a Bayesian beta-binomial model with correlated binary data (Diniz et al; 2010).⁸ For each simulated trial, the upper bound of the 95% central posterior credible interval constructed for the percentage of acceptable lens fittings for the test lens was compared to a margin of 80%. With the proposed sample size, at least 99% of the estimated 95% credible intervals had the lower bound above 80%.

Co-Primary Efficacy Endpoint Sample Size Calculations:

Distance Monocular Visual Acuity (logMAR) and CLUE Vision Scores

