14.5. Primary Analysis

Methodology regarding the plan for testing and/or handling statistical associations between co-primary safety and/or efficacy endpoints will be documented in the SAP.

Co-Primary Safety Analyses:

All primary safety analysis will be conducted on the safety population.

Grade 3 or Higher SLF

Grade 3 of Higher SLFs will be analyzed using a Bayesian beta-binomial model with correlated binary data.⁸

The Model:

Let \mathbb{Y}_1 and \mathbb{Y}_2 denote the binary outcomes of lens fit acceptance (Yes/No) in left and right eyes, respectively, across dispensing and follow-up visits when wearing the test lens. Considering the correlation, $\rho\rho$, between \mathbb{Y}_1 and \mathbb{Y}_2 , the distribution of the sum $YY = \mathbb{Y}_1 + \mathbb{Y}_2$ is obtained by the mixture of two variables. One of them follow a binomial distribution $BB\BBB(2, \rho\rho)$ with mixing probability $(1 - \rho\rho)$ and the other one follows a modified Bernoulli distribution, $MMBB\BBB(1 - \rho\rho)$, taking value 0 and 2 rather than conventional 0 and 1, with mixing probability $\rho\rho$:

$$PP(YY = yy | \rho\rho, \rho\rho) = (1 - \rho\rho)BB\BBB(2, \rho\rho)I_{AA1} + \rho\rho MMBB\BBB(1 - \rho\rho)I_{AA2},$$

where $I_{AA1} = \{0, 1, 2\}$, $I_{AA2} = \{0, 2\}$ and $\rho\rho$ is the probability of success (i.e., acceptable lens fitting).

To overcome the complexity of the mixture likelihood a latent variable ZZ_{ii} , $i = 1, 2$ is introduced in the model to indicate in which component of the model the observation yy_{ii} , $i=1, 2$, belongs to, that is,

$$ZZ = \begin{cases} 1, & \text{if the observation belong to the MBern}(p), \\ 0, & \text{if the observation belong to the Bin}(2, p) \end{cases}$$

The joint distribution of the augmented data (YY_{ii}, ZZ_{ii}) , $BB = 1, 2$, is given by

$$P(Y = y, Z = z | p, \rho) = \rho^{z_i} p^{y_i z_i / 2} (1 - p)^{(2 - y_i) z_i / 2} (1 - \rho)^{1 - z_i} \prod_{i=1}^2 p_{y_i}^{y_i(1 - z_i)} (1 - p)^{(2 - y_i)(1 - z_i)}$$

The probability p links to the regression variables through a logit transformation as follow:

$$\text{logit}(p) = \beta_0 + \beta_1 \text{lens}$$

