It is assumed that β_0 , β_1 and $\rho\rho$ to be independent with a non-informative prior $N(0, 1000)$ for β_0 and β_1 , and beta(0.5, 0.5) for $\rho\rho$. The Metropolis sampler algorithm as implemented in the SAS/STAT MCMC Procedure⁷ will be used to estimate the posterior distributions of the parameters $(\beta_0, \beta_1, \rho\rho)$. Inferences will be made based on a posterior credible interval for the relevant parameters.

Bayesian Estimation and Statistical Evaluation of Hypothesis:

Superiority of the test lens relative to the pre-defined threshold with respect to grade 3 or higher will be evaluated using Bayesian statistics.

Primary Safety Hypothesis 1:

The null and alternative hypotheses for evaluating superiority of the test lens relative to 5% are as follows:

$$H_0: \rho\rho_T \geq 5\%$$

$$H_A: \rho\rho_T < 5\%,$$

Clinical Study Protocol
Johnson & Johnson Vision Care, Inc.

where p_{pT} is the probability of a grade 3 or higher SLF across all study visits for test lens. Based on Bayesian posterior probability distribution of the proportion pp_{TT} , superiority is interpreted as 95% probability of test being statistically lower than the threshold of 5% (i.e., $p_{pT} < 0.05$). If the upper bound of the 95% central posterior credible interval is below 0.05, it can be concluded that there is 95% probability that the test lens is superior to 5% (statistically less than) based on the observed sample.

In the case of zero clinically significant SLF, a Bayesian hierarchical model accounting for zero-event problem will be considered.⁸

Acceptable Lens Fitting

Lens fit acceptance will be analyzed using a Bayesian beta-binomial model with correlated binary data.⁸

Bayesian Estimation and Statistical Evaluation of Hypothesis:

Superiority of the test lens relative to the pre-defined threshold with respect to acceptable lens fitting will be evaluated using Bayesian statistics.

Primary Safety Hypothesis 2:

The null and alternative hypotheses for evaluating superiority of the test lens relative to 80% are as follows:

$$\begin{aligned} H_0: p_{pT} &\leq 80\% \\ H_{AA}: p_{pT} &> 80\%, \end{aligned}$$

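### The N(0,1000) logit priors in section 14.5 are not neutral for a rare event: they lower the upper bound for slit-lamp findings, and the plan reports no pass rate at the 5% limit

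*Combined protocol and SAP*

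**What the plan says.** Section 14.5 models each subject's two eyes as a mixture: with probability ρ both eyes respond alike, otherwise they are independent with common probability p. "The probability p links to the regression variables through a logit transformation as follow": an intercept plus a lens term. The coefficients and ρ are taken "to be independent with a non-informative prior", N(0,1000), for the two coefficients "and beta(0.5, 0.5) for" ρ. The plan does not say whether 1000 is a variance or a standard deviation.

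The decision rule is "If the upper bound of the 95% central posterior credible interval is below 0.05". The same paragraph words it differently: "superiority is interpreted as 95% probability of test being statistically lower than the threshold of 5" per cent. If nothing is observed, the section adds: "In the case of zero clinically significant SLF, a Bayesian hierarchical model accounting for zero-event problem will be considered". It gives no further detail of that model for this endpoint.

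In section 14.2, "a total of 5000 replicating trials were simulated with a reference rate of 2% (worse-case scenario"), with an eye correlation of 0.70, and at least 99% of the intervals are reported to fall below 5%. Table 9 lists 100 subjects and 99% power. Sections 2.3 and 14.4 make this one of the two safety tests that must succeed before any efficacy hypothesis is tested.

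**The concern.** A very wide normal prior on the logit scale looks harmless but is not flat on p. It favours values of p near 0 and 1, so for a rare event it lowers the upper bound, and a lower bound is what passes this test. Historical rates are 0% (Table 8), so zero or a handful of findings is the expected result, and that is where the prior has most influence. Neither section reports how often a lens at the 5% limit would pass, and there is no prior sensitivity analysis. At stake are the error rate of the test that opens the whole testing sequence and the credibility of the upper bound that will be reported.

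**Working it through.** **Inputs.** Priors, mixture and pass rule: section 14.5. Eye correlation 0.70 and 2% rate: section 14.2. Sample size 100: Table 9. Completers 165 and enrolled 180: section 4.3. I read 1000 as a variance (SD 31.6 for one coefficient; variance 2000, SD 44.7, for the sum of two).

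**Model.** For a subject with 0, 1 or 2 affected eyes:

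- P0 = (1−ρ)(1−p)² + ρ(1−p)
- P1 = (1−ρ)·2p(1−p)
- P2 = (1−ρ)p² + ρp

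The posterior of (p, ρ) is proportional to P0^n0 · P1^n1 · P2^n2 times the prior, evaluated on a grid with ρ ~ Beta(0.5,0.5). A trial passes if the posterior probability of p ≥ 0.05 is below 0.025, which is the upper limit of a central 95% interval. Pass rates are exact sums over the multinomial counts, using test-lens data only.

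**The plan's own figure first.** Stated: at least 99% power at a true rate of 2%, correlation 0.70. Obtained with the planned prior: 54.5% at 100 subjects, 71.8% at 165, 76.1% at 180. Setting the correlation to 0 gives 62.9% at 100 and 86.1% at 165; correlation 0 with a 5% one-sided tail gives 78.7% at 100. No variant tried reproduces 99%. At 100 subjects and correlation 0.70, 99% is reached only at a true rate of about 0.2%.

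**What the prior does to p.** If η = logit(p) has density g(η), p has density g(logit p)/[p(1−p)]. With variance 1000, g at p = 5% (η = −2.94) relative to its peak is exp(−2.94²/2000) = 0.996. So g is practically constant, and the prior on p is close to 1/[p(1−p)].

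**Pass rate at a true rate of 5%, planned prior** (variance 2000 gives the same figures):

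| Subjects | Correlation | Pass rate |
|---|---|---|
| 165 | 0 | 2.9% |
| 165 | 0.3 | 3.5% |
| 165 | 0.5 | 4.0% |
| 165 | 0.7 | 4.9% |
| 165 | 0.9 | 4.8% |
| 100 | 0.7 | 6.4% |
| 180 | 0.7 | 4.7% |

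With both lenses in the model sharing ρ (165 subjects, correlation 0.70, 6,000 simulated trials per setting, control rate 1%, 2% or 5%), the rate is 4.2 to 4.6%, Monte Carlo standard error about 0.3 points.

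**How much of this is the prior.** At 165 subjects and correlation 0.70, Beta(0.5,0.5) on p gives 3.2% and Beta(1,1) gives 1.9%. The difference from Beta(0.5,0.5) is 4.9 − 3.2 = 1.7 points at 165, 4.2 − 3.4 = 0.8 at 175, and close to 1.8 at 180. At 165 subjects these two priors decide differently for only three outcomes, written as (subjects with one eye affected, subjects with both): (2,3), (4,2) and (9,0).

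**Zero findings.** With correlation 0.70 and a true rate of 1%, P0 = 0.3(0.9801) + 0.7(0.99) = 0.98703, and 0.98703^165 = 0.12. At 0.5%, P0 = 0.99351 and the chance is 0.34. In that event the upper bound at 165 subjects is 0.08 to 0.14% with the planned prior, 1.1% with Beta(0.5,0.5) and 1.7% with Beta(1,1). All three pass.

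**The case against.** **The benchmark.** The strongest reply is that the plan interprets success as 95% probability, which on its face is a 5% tail, and 4.9% does not exceed that. It sets no frequentist error rate for the safety tests, and a credible interval does not promise one. This stands as a limit on the claim. The operative rule is nevertheless the bound of a central interval, which demands 97.5% posterior probability, so the two statements do not agree.

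**Attribution and size.** A reader might infer that the prior alone makes the test clear an unsafe lens twice as often as promised. The documents do not support that: the ratio depends on choosing 2.5% as the benchmark and falls with lower correlation, and more than half of the 4.9% remains under Beta(0.5,0.5).

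**Prior mass.** It is also tempting to cite the 92.6 to 94.8% of prior mass lying below 5% or above 95%. Only 46 to 47% lies below 5%; the upper half plays no part here.

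**Small counts.** One might think that trials with one to four affected subjects are wrongly passed. At 165 subjects the planned prior and Beta(0.5,0.5) agree on every such outcome.

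**Zero events.** The plan foresees another model, and section 14.1 leaves detail to a stand-alone SAP that is not among the documents. That is fair, but the text commits only to considering it. For the same reason, the right statement is that the pass rate at 5% is not reported here, not that it was never examined.

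**Conclusion.** The point holds at moderate size. The prior described as non-informative leans toward passing: about 4.9% at the 5% limit with 165 subjects and correlation 0.70, against a 2.5% tail under the central-interval rule and no excess under the 95% probability wording. Of this, roughly 0.8 to 1.8 points at 165 to 180 subjects come from the prior. With zero findings the decision is unaffected, but the reported bound would be roughly a tenth of what Beta(0.5,0.5) gives and would mainly reflect the prior. The stated 99% power at 2% does not reproduce, so the section 14.2 simulation cannot be used to show that the test behaves well under this prior.

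These figures assume that 1000 is a variance (a standard deviation of 1000 would be flatter still on the logit), that the section 14.5 mixture generates the data, and, for the main figures, that only test-lens data are used. Because the counts are discrete, the rate moves with sample size: 4.2 to 5.2% over 150 to 185 subjects in steps of five.

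**What to change.** In section 14.5 and the SAP:

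- Put Beta(0.5,0.5) directly on the test-lens probability p_T and keep Beta(0.5,0.5) on the correlation. Give Beta(1,1) as a sensitivity analysis, or make it primary if at most 2.5% is wanted, because Beta(0.5,0.5) still gives about 3.2% at correlation 0.70.
- Use this model whether or not findings occur, in place of the data-triggered change of model. The prior is proper, so zero events pose no problem.
- Make the probability statement agree with the interval rule: either 97.5% posterior probability with the central 95% interval, or an explicit 5% one-sided tail.
- Rerun the section 14.2 simulation at 5% as well as 2%, report both pass rates, and correct the power in Table 9.

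The work is a wording change and a rerun of an existing simulation. The price is power. At 165 subjects and correlation 0.70, moving from the planned prior to Beta(0.5,0.5) takes it from 99.7% to 99.5% at a true rate of 0.5%, from 96.3% to 94.6% at 1%, and from 71.8% to 63.9% at 2%. Beta(1,1) costs more: 98.9%, 90.3% and 53.2% at the same rates. At the rates below 1% that the plan expects, the loss with Beta(0.5,0.5) is small.

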Visit 1: Lens Fittin #1		
Step	Procedure	Details
1.21	Toric fit assessment	
Record for each eye:
 
 1. The rotational position to the nearest degree 2. Lens stability with blinks 3. Toric fit acceptability. The toric lens fit will be designated as 'unacceptable' if either: 
 a. The lens ABSOLUTE ROTATION is greater than 20 degrees b. The LENS STABILITY WITH BLINK is greater than 5 degrees 
If one or both lenses demonstrate an unacceptable toric fit, the subject will be discontinued (proceed to final evaluation).

1.22	General lens fit assessment	
The fitting characteristics of the lens in both eyes will be assessed using a slit lamp. Lens position (centration, limbal exposure, edge lift) and movement (primary and up gaze as well as push-up) will be assessed. Fit acceptability is defined as any lens that does not display the following general fit characteristics:
 
 • Limbal exposure (presence of clear comea) in any direction of gaze. • Edge lift. • Insufficient movement in all three movement assessments (primary gaze, up-gaze and push-up test). • Excessive movement in primary gaze. 
If the general fit is unacceptable for either eye, the subject will be discontinued (proceed to exit evaluation).

1.23	Spherical over-refraction	
Perform monocular spherical over-refraction using duo-chrome to refine the endpoint as described in step 1.11 (the final spherical endpoint may be determined binocularly).
 
The spherical over-refraction must be plano in both eyes to continue.
 
If a non-plano over-refraction is found in either eye, the lens(es) must be refit with the indicated change in sphere power. If the indicated lens power is not available for either eye (e.g., outside the available SKU range), the subject will be discontinued (proceed to final evaluation).

Clinical Study Protocol
Johnson & Johnson Vision Care, Inc.

Visit 1: Lens Fittin #1		
Step	Procedure	Details

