14. STATISTICAL METHODS

14.1. General Considerations

Statistical Analysis will be undertaken by the sponsor or under the authority of the sponsor. A general description of the statistical methods to be implemented in this clinical trial is outlined below. More details will be included in the stand-alone Statistical Analysis Plan (SAP). The SAP will be developed and finalized prior to database lock.

All data summaries and statistical analyses will be performed using the SAS software Version 9.4 SAS Institute, Cary, NC⁷. Throughout the analysis of data, the results for each subject/eye will be used when available for summarization and statistical analysis. For the analysis of co-primary safety endpoints, unscheduled visits will be summarized separately and will not be excluded from the statistical analysis. However, for the analysis of co-primary efficacy endpoints and secondary endpoints, unscheduled visits will be summarized separately and excluded from the statistical analysis.

Summary tables (descriptive statistics and/or frequency tables) will be provided for all baseline variables, efficacy variables and safety variables as appropriate. Continuous variables will be summarized with descriptive statistics

Clinical Study Protocol
Johnson & Johnson Vision Care, Inc.

(n, mean, standard deviation(SD), median, minimum and maximum). Frequency count and percentage of subject.s or eyes within each catego1y will be provided for categorical data.

Summaries will be presented by separately for each time point (baseline, fitting and 1-week follow-up) and will be perfo1med separately by completion status (Safety Population, Per-Protocol Population or Intent-to-treat, when appropriate).

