Toric Lens Orientation and Rotational Stability at Least 15- Minutes Following Lens Settling

Absolute toric lens orientation (degrees) will be dichotomized as $Y=1$ if the absolute lens orientation (degrees) $\leq 10^\circ$ and $Y=0$, otherwise. Rotational stability will be quantified by lens stability with blinks (degrees). Lens stability will be dichotomized as $Z=1$ if the lens stability with blinks (degrees) $\leq 5^\circ$ and $Z=0$, otherwise.

Y and Z will be analyzed separately using a generalized linear mixed model with a binary distribution and the logit as the link function. Sequence of lens wear, lens type and period will be included in the model as fixed effects. Subject characteristics such as, gender, age and/or cylinder power may be included in the model if appropriate. Site ID and subject nested within site will be included in the model as random effects (G-side). The residual error between measurements within the same subject across study period will be modeled using an unstructured (UN) covariance structure. If the model fails to converge with a UN covariance, then a compound systemic (CS) covariance structure will be used. The Kenward and Roger Method will be used for the denominator degrees of freedom.¹¹

Primary Efficacy Hypothesis 2:

The null and alternative hypothesis to test for superiority of absolute lens orientation $\leq 10^\circ$ for the test lens relative to the threshold 80% are as follows:

$$\begin{aligned} H_{H_0}: pp_{TTTTTTTT} &\leq 80\% \\ H_{H_A}: pp_{TTTTTTTT} &> 80\% \end{aligned}$$

Where $pp_{TTTTTTTT}$, represents the population percentage for the percentage of eyes wearing the test lens with absolute lens orientation $\leq 10^\circ$. Superiority will be declared if the lower limit of the 95% CI is above 80.

Depending on the observed response rates for the percentage of subjects' eyes with absolute lens orientation $\leq 10^\circ$ and the percentage of subjects' eyes with lens stability with blinks $\leq 5^\circ$, a Bayesian hierarchical model accounting for zero event problem may be considered (i.e., 0% of eyes with toric rotation $>10^\circ$ [or lens stability $>5^\circ$]) . Details of this model will be provided in the stand-alone SAP.

Primary Efficacy Hypothesis 3:

The null and alternative hypothesis to test for superiority of lens stability with blinks $\leq 5^\circ$ for the test lens relative to the threshold 80% are as follows:

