$$\begin{aligned} H_{H_0}: pp_{TTTTTTTT} &\leq 80\% \\ H_{H_A}: pp_{TTTTTTTT} &> 80\% \end{aligned}$$

Where $pp_{TTTTTTTT}$, represents the population percentage for the percentage of eyes wearing the test lens with lens stability with blinks $\leq 5^\circ$. Superiority will be declared if the lower limit of the 95% CI is above 80.

CLUE Vision Scores

CLUE vision scores after 1 week of lens wear will be analyzed using a linear mixed model adjusting for baseline scores as a covariate. Sequence of lens wear, lens type and period will be included in the model as fixed effects. Subject characteristics such as, gender, age and/or cylinder power may be included in the model if appropriate. Site ID will be included in the model as a random effect (G-side). The residual error between measurements within the same subject will be modeled using an unstructured (UN) covariance structure. If the model fails to converge with a UN covariance, then a compound systemic (CS) covariance structure will be used. The Kenward and Roger Method will be used for the denominator degrees of freedom.¹¹ CLUE Vision Scores estimates for each study lens will be estimated using 95% confidence intervals (CI) constructed for the least-square means (LSM).

Clinical Study Protocol
Johnson & Johnson Vision Care, Inc.

Primary Efficacy Hypothesis 4:

The null and alternative hypothesis to test for superiority of CLUE vision score for the test lens relative to the threshold 62 are as follows:

$$\begin{aligned} H_0: \mu_{TTTTTTTT} &\leq 62 \\ H_A: \mu_{TTTTTTTT} &> 62 \end{aligned}$$

Where $\mu_{TTTTTTTT}$, represents the population mean for test lens after 1 week of lens wear with respect to CLUE vision scores. Superiority will be declared if the lower limit of the 95% CI is above 62.

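### The toric orientation and stability tests concern a population percentage of eyes, but the logit mixed model in Section 14.5 is conditional on subject and site, and the step from one to the other is not stated

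*Combined protocol and SAP*

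**What the plan says.** Section 14.5 dichotomises orientation (Y, at most 10 degrees) and stability with blinks (Z, at most 5 degrees), both taken after settling at the fitting visit. The model is given as: "Y and Z will be analyzed separately using a generalized linear mixed model with a binary distribution and the logit as the link function". Sequence, lens and period are fixed effects. On clustering it says: "The residual error between measurements within the same subject across study period will be modeled using an unstructured (UN) covariance structure". It also says: "Site ID and subject nested within site will be included in the model as random effects (G-side").

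The tested quantities are marginal. For Hypothesis 2 the parameter "represents the population percentage for the percentage of eyes wearing the test lens with absolute lens orientation" of at most 10 degrees. For Hypothesis 3 it "represents the population percentage for the percentage of eyes wearing the test lens with lens stability with blinks" of at most 5 degrees. Each test passes if the lower limit of a 95% CI is above 80, and the construction of that interval is not described.

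Elsewhere the plan names its estimator: CIs for least-square means for visual acuity and the CLUE scores (Sections 14.5 and 14.6), and an odds-ratio CI for the exploratory binary items (Section 14.7). Section 14.1 adds: "More details will be included in the stand-alone Statistical Analysis Plan (SAP"). For the toric endpoints, Section 14.5 specifically defers only the zero-event Bayesian model.

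**The concern.** With an identity link, as for visual acuity, the mean at zero random effect equals the population mean, so the G-side subject term is harmless. With a logit link it does not. The inverse logit of the lens estimate gives the success probability for an eye of a subject at the centre of the random-effect distribution, at a central site. When success is common and the two eyes of a subject are correlated, this lies above the proportion of eyes in the population that succeed.

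The hypotheses concern the latter. An analyst who follows the text and takes the usual back-transformed estimate would compare a different, higher quantity with 80%. These are two of the four co-primary efficacy tests, and Section 14.4 requires all co-primary tests to pass before any secondary hypothesis is tested.

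**Working it through.** **Inputs.** Threshold 80%; planned rates 97.5% (orientation) and 98% (stability); between-eye correlation 0.70 (all Section 14.2); 165 completers (Section 4.3). The correlation is a planning assumption, so 0.10 to 0.70 is shown. The lower limit of a two-sided 95% CI is nominally a 2.5% one-sided test.

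**1. The plan's own figures.** Section 14.2 sizes both endpoints with the correlated-binomial model written out in Section 14.5. For Y successes among a subject's two eyes:

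- P(Y=2) = (1-rho)p^2 + rho p
- P(Y=1) = 2(1-rho)p(1-p)
- P(Y=0) = (1-rho)(1-p)^2 + rho(1-p)

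E(Y)/2 = [2(1-rho)p + 2 rho p]/2 = p, so p is the marginal percentage of eyes. With rho = 0.70, the stated priors and success defined as a 2.5% posterior quantile above 0.80, exact enumeration gives 99.4% power for 40 subjects at 97.5% and over 99.9% for 100 subjects at 98%. Table 9 gives 99% for both. The sizing reproduces, and it used a marginal p.

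**2. What the mixed model's back-transformed estimate targets.** Take logit P(success | u) = b + sigma u, with u standard normal. The population rate is m = E[expit(b + sigma u)] and the eye correlation is r = Var[expit(b + sigma u)] / (m(1-m)). Solving for m = 0.80:

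| r | sigma | expit(b), zero subject effect |
|---|---|---|
| 0.10 | 0.84 | 82.9% |
| 0.30 | 1.76 | 88.9% |
| 0.50 | 3.01 | 95.0% |
| 0.70 | 5.55 | 99.3% |

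Hand check at 0.70: b = ln(0.9927/0.0073) = 4.91. The usual attenuation approximation gives 4.91/sqrt(1 + 0.346 x 5.55^2) = 4.91/3.41 = 1.44, and expit(1.44) = 0.81, close to the required 0.80.

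**3. Consequence for the orientation test, if that estimate is used.** Trials were simulated with 165 subjects, complete data and a true 80%. At correlation 0.70 the pass rate exceeded 2.5% under every fitting method tried, but ranged from 12% to 99.7%. It depended on the likelihood used, on whether the residual term was included, on the correlation between lenses and on the control rate. At 0.30 the runs gave 31% to 58%; at 0.10, 1% to 10%. Most mixed-model scenarios had only 100-120 runs and an assumed 11 sites of 15. They show the direction and the dependence on unstated choices; they do not give a rate for this trial.

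**4. A marginal test for comparison.** At a true 80% (82 + 83 subjects, 40,000 runs, no site effect), a CI formed on the logit of the test-lens percentage averaged over the two sequences passed 2.0%, 2.3% and 2.2% of the time at correlation 0.70, 0.30 and 0.10. A plain proportion-scale CI passed 3.7%, 3.5% and 3.5%. If sites differ and the standard error is at subject level only, the logit-scale version rises from 2.2% to 3.7%, 6.7% and 10.2% at assumed site correlations of 0.02, 0.05 and 0.10. Site must therefore enter the standard error.

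**5. Why stability is not quantified.** Under Section 7.2, step 1.21, a toric fit is unacceptable if "The LENS STABILITY WITH BLINK is greater than 5 degrees", which is exactly Z=0, and "If one or both lenses demonstrate an unacceptable toric fit, the subject will be discontinued". Visit 3 repeats the step. At a true 80% and correlation 0.70, both eyes pass in 0.80^2 + 0.70 x 0.80 x 0.20 = 0.752 of subjects, so 24.8% would be discontinued at the test-lens fitting. Whether their Z=0 eyes are analysed depends on the efficacy population, which Section 14.5 does not state. A complete-data calculation does not apply.

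**The case against.** The best defence is that Section 14 describes itself as general and leaves detail to a stand-alone SAP, to be finalised before database lock. Deriving a percentage from a mixed model is ordinary SAP content. That stands: the point concerns an omission in the supplied text, not an error known to be carried into the analysis. A reader might infer that the trial will use the zero-random-effect estimate and therefore has a grossly inflated error rate. The documents never say so, and the simulated range is too wide to support any figure.

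Second, the planned rates are far from the threshold. At a true 97.5% and correlation 0.70, the lowest observed rate in 20,000 simulated trials of 165 subjects was 91.5%. A reader might infer that the planned power or the likely conclusion is in doubt; it is not. Carrying the correlation of 0.70 down to a rate of 80% is also an extrapolation, since the plan pairs it with rates of 97.5-98%.

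Third, a reader might extend the orientation figures to stability. Step 1.21 and the unstated population prevent that. Orientation is less affected, but fits rotated by more than 20 degrees are also discontinued, in a proportion the documents do not give, so the complete-data figures are approximate there too.

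What survives is that the model's default output and the hypothesis are different quantities. Sizing used one and the analysis model estimates on the scale of the other. That is more than missing detail.

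**Conclusion.** The point holds as a specification gap that should be closed before database lock. For orientation, the ordinary back-transformed estimate would overstate a population 80% by 2.9 points at eye correlation 0.10 (82.9 - 80) and by 19.3 points at 0.70 (99.3 - 80), assuming logistic-normal subject effects. If it is used and eyes are strongly correlated, a lens truly near 80% could pass more often than the nominal 2.5%. The excess is small or absent at correlation 0.10, and its size elsewhere depends on the estimator and on correlations that the documents do not give. For stability, the same mismatch between model and tested quantity exists, without a numerical claim.

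**What to change.** In the toric part of Section 14.5, state that both tests concern the marginal percentage of eyes for the test lens, and name one way of obtaining it:

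- mixed-model probabilities averaged over the random effects, with a delta-method or bootstrap CI;
- the correlated-binomial model already used for sizing; or
- a marginal model (GEE or R-side covariance only).

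Whichever is chosen:

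- Keep sequence, period and lens in the model.
- Account for site in the standard error, for example by site-level clustering with a small-sample correction.
- Form the 95% CI on the logit scale.
- Define the estimate for the first-period-only rule in Section 4.2, where only one sequence has worn the test lens.
- Keep the zero-event provision and extend it to a sequence group with no failures. Under the sizing model, a subject has no failing eye with probability p^2 + rho p(1-p). At 97.5% this is 0.9506 + 0.70 x 0.0244 = 0.9677. The chance that at least one of groups of 82 and 83 has no failures is 0.9677^82 + 0.9677^83 - 0.9677^165, about 12.9%; at 98% it is 21.7%.
- State the analysis population for both endpoints.

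The cost is wording and code, with no change to sample size or conduct. Intervals widen somewhat if sites differ. Power at 97.5% stays at about 94-100% with site-level clustering, assuming 11 sites of 15 and site correlation 0 to 0.10. Under the first-period rule, with about 82 subjects and no site effect, power at a true 90% would be about 72%, against 96.9% with 165.
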